**Study design / observational study period**

Retrospective, observational, medical record review

**Figure 1. Study schematics.****3.1.1. Patient Identification Process and Eligibility Verification**

Staff at participating sites will consecutively review their LN patients' medical charts to pre-identify potential patients who meet the study's preliminary selection criteria and might be considered eligible to participate in the study. Identified patients who are potentially eligible will be contacted over the phone or approached onsite at the patient's routine care visit if the visit falls within the study enrolment timelines. When contacting the patient, site staff will review the main study informed consent form (ICF) with each patient to explain the study design, which will include a two-time prospective patient survey, prospective data abstraction from medical charts for a period of a year, as well as a one-time retrospective data abstraction from their medical chart. Additionally, site staff will answer any questions patients may have at this time about the study. Patients will be asked to confirm study interest verbally.

Site staff will maintain a master list of patients invited to participate in the study (screening log) to assess the correspondence of the sample to the general population of potentially eligible LN patients at the site.

**3.1.2. Patient Consent and Patient Survey**

Eligible patients who provide verbal consent will receive a written informed consent form and asked to review and sign following the discussion of the study with the site staff and all queries resolved. Upon signing of the consent form the patient will be asked to complete the first patient survey during their first routine care visit after signing of the consent form. The second patient survey will be completed approximately 12 months after the completion of the first survey. In routine care, this would typically be Visit 5 from the enrolment period.

### 3.1.3. Retrospective Medical Chart Review

Site staff will perform a one-time data abstraction from the medical charts of patients who sign the consent form and complete the first patient survey. Available data in the charts as part of usual care from diagnosis, or up to (12) twelve months prior to enrolment will be abstracted (as outlined in [Section 3.2.2](#)). Data abstracted will be recorded directly in the eCRF.

### 3.1.4. Prospective Medical Chart Data Collection

Site staff will be asked to abstract data from medical charts of patients who have completed the first patient survey. Data will be abstracted after each patient visit based on their routine care visits. Data abstracted will be recorded directly in the eCRF. A typical LN patient visits the physician every 3 months. In total there will be 5 visits ([Figure 1](#)).

- a. Visit 1: Enrolment visit
- b. Visit 2: 3-month follow-up after Visit 1
- c. Visit 3: 6-month follow-up after Visit 1
- d. Visit 4: 9-month follow-up after Visit 1
- e. Visit 5: last 12-month follow-up visit after Visit 1

We will aim for the data collection visits to be near the 3,6,9,12-month time points, however, since this is a real-world evidence study the frequencies of visits may vary from one patient to another. Therefore, we will take the closest available visit to our study time points. If a patient misses a visit, we will analyse based on available data and assume clinical status did not change. This would allow to minimise the influence of the study procedures on the typical schedule of patient and associated healthcare resource utilisation.

### 3.1.5. One-Time Physician Survey

A brief, one-time physician survey will be used to collect site-level data on overall practice, population of patients with LN, and LN-related treatment patterns. Sites will be asked to complete and return the survey prior to the last subject last visit date ([Appendix 5. Physician Practice Form](#)).

### 3.1.6. Medical Cost / HCRU

Site staff will be asked to perform abstraction of data on HCRU from the medical charts of patients who sign the consent form and complete the first patient survey. Other data will be collected at enrolment and prospectively. These include number of laboratory tests, number of dialyses and use of imaging techniques, hospitalisations in the intensive care unit (ICU)/hospitalisations. Data abstracted will also be recorded directly in the eCRF.

Data related to the unitary cost of individual healthcare resources will be collected retrospectively at the end of prospective observation. The source of the cost information will be collected for each country separately. For each country, the payer perspective shall be taken (Ministry of Health or the tender price for the relevant payer).

The type of unitary costs will be divided for each country in laboratory tests, biopsy and imaging, medical costs, medical visits costs and hospitalisation costs. More details will be further developed in the statistical analysis plan (SAP).

The cost of illness shall be stratified by disease activity (SELDALI-2K).

The prices will be taken by the end of the year for each country/institution for each resource; if any price modification has occurred during the year, an average price will be considered for the related resource.

Inflation will not be considered since the study period is only for one year.

### **3.2. Data Source / Data Collection**

Data collection will occur by physician abstraction of patient medical chart data onto the study eCRFs which were developed by GSK and the clinical research organisation (CRO). All data instruments are field-tested prior to initiation of data collection.

#### **3.2.1. Physician Practice Profile Form**

After being screened for study eligibility and successfully recruited, each physician will be assigned a unique identifier, and the PPPF will be completed. This form will be used to gather specific physician practice information including:

- 1) Clinical practice and investigator profile
- 2) Practice setting (community-based, hospital-based or other)
- 3) Practice type (solo; single specialty group or multi-specialty group with number of rheumatologists quantified)
- 4) Years in practice
- 5) Estimated currently managed total patients and SLE and LN patients
- 6) Patients' role in SLE treatment decisions

### 3.2.2. Retrospective Data Collection and Prospective Data Collection

Participating physicians will assign a unique identifier to each patient selected for inclusion in the study. This identifier will be used to facilitate follow-up on data queries and data entry validation. The date of chart data abstraction will be tracked separately by the eCRF vendor.

- e. Most recent serological findings such as: antiphospholipid antibody tests (anticardiolipin, anti-beta 2 glycoprotein 1 [GP1] and lupus anticoagulant), antiC1q, low-complement (C3/C4), positive anti-double-stranded deoxyribonucleic acid (anti-dsDNA) (IU/mL), anti-U1-RNP, anti-Sm antibody, anti-Rib, and anti-Scl-70

- f. Renal assessments, such as urinary protein to creatinine ratio (UPCR) or 24-hour proteinuria (mg/24-hr) or urine sediment (activity), serum creatinine (mg/dL), and estimated glomerular filtration rate (eGFR) or measured glomerular filtration rate (GFR) (if eGFR is not available) with date of assessment

8) Active non-renal clinical manifestations of SLE (such as mucocutaneous, central nervous system, constitutional, cardiopulmonary, gastrointestinal, hematologic, musculoskeletal, and vasculitis)

- a. Type and date of resolution, if applicable

9) Most recent total Systemic Lupus Erythematosus Disease Activity Index (SLEDAI), such as SLEDAI or SLEDAI-2K ([16](#)), [Appendix 2](#)

10) Renal remission: defined as proteinuria of  $<0.7$  g/d or  $<0.5$  g/d or at physicians' discretion

11) Renal biopsy:

- a. Activity index
- b. Chronicity index
- c. Number of glomeruli

**Prospective data collection from enrolment (0, 3, 6, 9, 12 months)**

Variables include but are not limited to ([Appendix 1](#)):

- 1) Non-renal and renal clinical manifestations at period start with clinical improvement/worsening assessment at period end
- 2) Changes in disease activity assessment tools used (such as SLEDAI-2K)
- 3) Refractory SLE: defined as inefficacy of cyclophosphamide, use of rituximab, splenectomy, or inefficacy of  $\geq 2$  immunosuppressives (methotrexate, leflunomide, abatacept, anti-TNF, azathioprine, mycophenolate mofetil, and/or mycophenolic acid)
- 4) Renal remission: defined as proteinuria of  $<0.7$  g/d or  $<0.5$  g/d or at physician discretion
- 5) Renal biopsy:
  - a. Activity index
  - b. Chronicity index
  - c. Number of glomeruli
- 6) Changes linked to the primary treatment of the disease:
  - a. Adjustment of the dose by 20% or more, and
  - b. Change happening for longer than 1 month, or
  - c. Change or addition in the type or group of medication (immunosuppressants, biologics, anti-malarial, and steroids)
- 7) Laboratory tests:
  - a. Haematology: white blood cell count ( $\times 10^9/L$ ), haemoglobin (g/dL), platelet count ( $\times 10^9/L$ ), erythrocyte sedimentation rate (mm/hour), C-reactive protein (mg/L)
  - b. Liver function tests
  - c. Lipid profile
  - d. Plasma albumin

- e. Most recent serological findings such as: antiphospholipid antibody tests (anticardiolipin, GP1 and lupus anticoagulant), antiC1q, low-complement (C3/C4), positive anti-dsDNA (IU/mL), anti-U1-RNP, anti-Sm antibody, anti-Rib, and anti-Scl-70
- f. Renal assessments, such as UPCR or 24-hour proteinuria (mg/24-hr) or urine sediment (activity), serum creatinine (mg/dL), and eGFR or measured GFR (if eGFR is not available) with date of assessment

8) HCRU (number of laboratory tests, number of dialyses and use of imaging techniques, ICU hospitalisations/hospitalisations, outpatient visits)

### 3.2.3. Prospective Patient Survey: HRQoL

The 36-Item Short Form Health Survey (SF-36) has been selected as a standard tool, utilized in past studies in patients with lupus nephritis and is widely used in both clinical and real-world research. The tool is comprehensive and recognized by multiple experts in rheumatology as the optimal validate tool to measure quality of life in clinical practice.

The 36-Item Short Form Health Survey (SF-36) is a 36-item QoL questionnaire covering 8 health domains: physical functioning (10 items), bodily pain (2 items), role limitations due to physical health problems (4 items), role limitations due to personal or emotional problems (4 items), emotional well-being (5 items), social functioning (2 items), energy/fatigue (4 items), and general health perceptions (5 items). The questionnaire is available in Arabic and English versions. The average time to complete the questionnaire is 5 to 10 minutes.

Each patient will complete an SF-36 form ([17](#)) at enrolment (Visit 1) and at the last visit (Visit 5). It will be completed by the patient in Arabic, or in English in case he/she does not understand Arabic. Once completed, the site staff will enter data in the eCRF.

Scores for each domain range from 0 to 100, with a higher score defining a more favourable health state ([Appendix 3](#) and [Appendix 4](#)).

### 3.3. Study Population

Study participants are patients with lupus nephritis as defined by physician per patient hospital records prior to the enrolment visit or at diagnosis. Retrospective data of patients with diagnosed LN who made at least one centre visit during 12 months prior to the enrolment visit or at diagnosis of LN who fulfil inclusion/exclusion criteria will be abstracted from chart records. The data will be consecutively extracted from paper or electronic records were available. Based on our sample size assumptions and power calculations the study population will aim to recruit 50% of patients with renal remission and 50% of patients with no renal remission at the time of enrolment.

### 3.3.1. Eligibility Criteria

Patient selection and eligibility for the study at the time of baseline enrolment were determined by the following inclusion/exclusion criteria.

#### 3.3.1.1. Inclusion Criteria

For inclusion into the study, all the following inclusion criteria must be fulfilled by the patients:

- 1)  $\geq$ age of 18 years
- 2) Clinician diagnosed LN patient
- 3) At least one visit to the investigational centre during 12 months prior to the baseline visit, recorded in medical documentation
- 4) Literacy in English or Arabic allowing to fully comprehend the written informed consent and study-specific patient reported questionnaires
- 5) Written informed consent by the patient

#### 3.3.1.2. Exclusion Criteria

Patients are not eligible for inclusion if they fulfil the following non-inclusion criteria:

- 1) Incomplete medical records to be able to assess the disease severity or absence of any of the following renal laboratory results from the medical record within the last (12) twelve months:
  - a. UPCR or 24-hour proteinuria or urine sediment (activity)
  - b. Serum creatinine or eGFR; or measured GFR, if eGFR is not available
- 2) Current or medical history of:
  - a. Congenital or acquired immunodeficiency
  - b. Malignancy in active treatment phase
  - c. Acute viral infection, such as HIV infection, requiring hospitalisation

### 3.3.2. Sample Size / Power Calculations

As other similar research recruited a sample size ranging between 200 and 300 patients (18,19) the decision was made to proceed with 200 sample size in this research. This sample size would provide a significant power to interpret the results of the study. In addition, due to overall budget

constraints the maximum number of participants allocated for the study has been determined as 200.

Based on the sample size determination using Slovin's formula and assuming the total SLE population in Gulf countries is 5,600 patients, while 40% of SLE patients manifest with lupus nephritis (LN), the entire LN population size was estimated as 2,240 patients disease onset ([1](#)).

The margin of error (significance level), denoting the allowed probability of committing an error in selecting a small representative of the population, is 0.067 for the 93% of confidence that the data are going to be reflective of the entire LN population, given the assumptions of 200 LN patients, required to achieve this significance level ([20](#)).

Significance of the adverse factors, impacting the data accuracy and completeness, will be assessed during the data acquisition and may result in respective adjustments to the sample size.

In addition, taking into account our secondary hypothesis on the association between clinical factors, biomarkers, treatment and renal remission, a sample size of 200 observations (of which 65% are in not in renal remission=0 and 35% are in renal remission=1) achieves 80% power at a 0.050 significance level to detect a change in Prob(Y=1) from the baseline value of 0.200 to 0.385 ([Table 1](#)). This change corresponds to an odds ratio of 2.508.

**Table 1.** Tests for the odds ratio in logistic regression with one binary X and other Xs  
(Wald Test) (21)**Numeric Results**

Power	N	Pcnt N X=1	P0	P1	Odds Ratio	R Squared	Alpha	Beta
0.80000	200	35	0.200	0.385	2.508	0.000	0.050	0.20000
0.80000	200	35	0.200	0.409	2.770	0.200	0.050	0.20000
0.80000	200	35	0.200	0.444	3.199	0.400	0.050	0.20000
0.80000	200	35	0.200	0.504	4.065	0.600	0.050	0.20000
0.80000	200	35	0.200	0.643	7.200	0.800	0.050	0.20000
0.90000	200	35	0.200	0.418	2.871	0.000	0.050	0.10000
0.90000	200	35	0.200	0.446	3.216	0.200	0.050	0.10000
0.90000	200	35	0.200	0.487	3.791	0.400	0.050	0.10000
0.90000	200	35	0.200	0.555	4.985	0.600	0.050	0.10000
0.90000	200	35	0.200	0.707	9.644	0.800	0.050	0.10000
0.80000	200	35	0.300	0.501	2.342	0.000	0.050	0.20000
0.80000	200	35	0.300	0.525	2.582	0.200	0.050	0.20000
0.80000	200	35	0.300	0.561	2.981	0.400	0.050	0.20000
0.80000	200	35	0.300	0.620	3.808	0.600	0.050	0.20000
0.80000	200	35	0.300	0.752	7.094	0.800	0.050	0.20000
0.90000	200	35	0.300	0.533	2.666	0.000	0.050	0.10000
0.90000	200	35	0.300	0.561	2.984	0.200	0.050	0.10000
0.90000	200	35	0.300	0.602	3.524	0.400	0.050	0.10000
0.90000	200	35	0.300	0.668	4.685	0.600	0.050	0.10000
0.90000	200	35	0.300	0.808	9.836	0.800	0.050	0.10000
0.80000	200	35	0.400	0.606	2.308	0.000	0.050	0.20000
0.80000	200	35	0.400	0.630	2.554	0.200	0.050	0.20000
0.80000	200	35	0.400	0.665	2.972	0.400	0.050	0.20000
0.80000	200	35	0.400	0.721	3.877	0.600	0.050	0.20000
0.80000	200	35	0.400	0.843	8.080	0.800	0.050	0.20000
0.90000	200	35	0.400	0.637	2.634	0.000	0.050	0.10000
0.90000	200	35	0.400	0.664	2.965	0.200	0.050	0.10000
0.90000	200	35	0.400	0.703	3.543	0.400	0.050	0.10000
0.90000	200	35	0.400	0.764	4.859	0.600	0.050	0.10000
0.90000	200	35	0.400	0.891	12.225	0.800	0.050	0.10000

**Report Definitions**

Power is the probability of rejecting a false null hypothesis. It should be close to one. N is the size of the sample drawn from the population. Pcnt N X=1 is the percentage of the population in which X = 1. P0 is the response probability at the mean of X. P1 is the response probability when X is increased to one standard deviation above the mean. Odds Ratio is the odds ratio when P1 is on top. That is, it is  $[P1/(1-P1)]/[P0/(1-P0)]$ . R-Squared is the R2 achieved when X is regressed on the other independent variables in the regression. Alpha is the probability of rejecting a true null hypothesis. Beta is the probability of accepting a false null hypothesis (21).

The sample size calculation was computed by PASS® version 2019.

## 4. DATA ANALYSIS CONSIDERATIONS

### 4.1. Analysis Population

Analyses will be based on the “all subjects enrolled (ASE)” population. This includes all subjects who meet the inclusion or exclusion criteria

### 4.2. Protocol Deviation

No per-protocol population is included in this study.

Any protocol deviations will be documented and tracked by the study team. Any lost to follow up will not be replaced if it happens after the third month of recruitment. All efforts will be done by the investigator to reach out to the patient who is lost to follow up. Analysis of data associated with visits will happen according to data analysis planned, except for HCRU.

The number of patients who do not meet the inclusion and exclusion criteria will be reported.

### 4.3. Interim Analysis

No interim analysis is planned for this study.

### 4.4. Data Analyses

#### 4.4.1. General Considerations for Data Analysis

Variables will be summarised using the mean±standard deviation along with the median, interquartile range, smallest and largest observations for continuous numeric variables such as age, body weight at SLE diagnosis, and HRQoL. For categorical variables such as gender, race, and current diagnosis, frequency distributions (basically the frequency and percentage in each category) will be used.

#### 4.4.2. Primary Analysis

The primary objective is to describe patient profile, demographic features, clinical manifestations, comorbidities, severity, treatments and HRQoL of LN patients across 5 Gulf countries. The analysis of the primary objective will be carried out on the ASE population and includes using summary statistics as described above in [Section 4.4.1. General Considerations for Data Analysis](#) at each time point the variables are collected.

#### 4.4.3. Secondary Analysis

The first secondary objective is to describe refractory LN cases, involving rituximab, and to assess changes in serological markers of disease activity (including anti-nuclear antibody, anti-dsDNA antibody and complement levels) over the treatment period. This will be achieved by first using summary statistics as per the general consideration of data analysis section at each time point. To assess one-year changes in numeric variables, the paired t-test or Wilcoxon signed rank test will be used while the McNemar's test will be used for changes in categorical variables. In addition, repeated measures analysis will be used to look at changes over the whole time period.

The second secondary objective is to assess the association between clinical factors (disease activity), biomarkers (inflammatory markers and hematological markers), treatment (type and duration of therapy) and renal remission. The variables included in the model will be taken from the measures closest to the time of enrolment. For continuous variables, the nonparametric Wilcoxon test will be used for assessing differences between the patients who attained renal remission versus patients who did not attain renal remission, while the chi-square test will be used for dichotomized variables. Statistically significant factors will be included in the multivariate logistic regression models with renal remission as the dependent variable. Odds ratio and corresponding 95% confidence intervals (CIs) will be presented.

The third secondary objective is to assess impact of LN on HRQoL over a one-year period after diagnosis or enrolment. This will be achieved by looking at changes in the SF-36 physical and mental components, and the total score at one year using the paired t-test or Wilcoxon signed rank test for non-normal distribution. Changes over all the time period will be assessed using repeated measures analysis.

The fourth secondary objective is to estimate HCRU and direct medical cost, associated with LN management across 5 Gulf countries over a one-year period. This will be carried out as per [Section 4.5. Cost Evaluation](#). Generating an estimate for the average HCRU and direct medical cost and creating the 95% CIs for those will be carried out for each country.

The number and proportion of patients with missing data will be presented. Listwise missing will be used during data analysis. All data analyses will be done using IBM-SPSS (version 26, Armonk NY). A *p*-value of 0.05 or less will be considered statistically significant.

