**2. Compared to one year ago, how would you rate your health in general now?**

1 - Much better now than one year ago

2 - Somewhat better now than one year ago

3 - About the same

4 - Somewhat worse now than one year ago

5 - Much worse now than one year ago

**The following items are about activities you might do during a typical day. Does your health now limit you in these activities? If so, how much?**

	Yes, limited a lot	Yes, limited a little	No, not limited at all
3. Vigorous activities, such as running, lifting heavy objects, participating in strenuous sports	 1	 2	 3
4. Moderate activities, such as moving a table, pushing a vacuum cleaner, bowling, or playing golf	 1	 2	 3
5. Lifting or carrying groceries	 1	 2	 3
6. Climbing several flights of stairs	 1	 2	 3
7. Climbing one flight of stairs	 1	 2	 3
8. Bending, kneeling, or stooping	 1	 2	 3
9. Walking more than a mile	 1	 2	 3
10. Walking several blocks	 1	 2	 3
11. Walking one block	 1	 2	 3
12. Bathing or dressing yourself	 1	 2	 3

**During the past 4 weeks, have you had any of the following problems with your work or other regular daily activities as a result of your physical health?**

	Yes	No
13. Cut down the amount of time you spent on work or other activities	 1	 2
14. Accomplished less than you would like	 1	 2
15. Were limited in the kind of work or other activities	 1	 2
16. Had difficulty performing the work or other activities (for example, it took extra effort)	 1	 2

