2.2. Secondary Objectives

2.2.1. Secondary objective 1

To describe refractory LN cases, involving rituximab, and to assess changes in serological markers of disease activity (including anti-nuclear antibody, anti-dsDNA antibody and complement levels) over the treatment period.

2.2.2. Secondary objective 2

To assess the association between clinical factors, biomarkers, treatment, and renal remission.

2.2.3. Secondary objective 3

To assess impact of LN on HRQoL over a one-year period after diagnosis or enrolment.

2.2.4. Secondary objective 4

To describe LN HCRU and direct medical cost, associated with LN management across 5 Gulf countries over a one-year period.

2.2.5. Secondary objective 5

CCI

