4.5. Specific Analyses

4.5.1. Analysis of the primary objective

Patient demographics will be summarised using the methods presented in the general consideration section (see Table 1). Similar analysis will be done for the clinical manifestations, comorbidities, severity, treatments and HRQoL of LN patients over one year (Tables 2-5).

4.5.2. Analysis of secondary objective 1

Summary statistics will be used to describe refractory LN cases and the independent t-test or Wilcoxon signed rank test along with repeated measures analysis will be used to test for changes in serological markers of disease activity at one year and over the treatment period. Changes in categorical variables at one-year period will be tested using the McNemar's test (see Table 6).

4.5.3. Analysis of secondary objective 2

Univariate and multivariate logistic regression with renal remission as the dependent variable and clinical factors and treatment as the independent variables. Odds ratios and 95% confidence intervals (CIs) will be presented. Variables with a p-value of 0.25 or less along with known associated factors with renal remission will be used to build the final multivariate model. The final multivariable model will contain only significant factors or those who have confounding effect on others in the model.(see Table 7).

4.5.4. Analysis of secondary objective 3

Changes in SF-36 total score from baseline to one year will be test for significance using the paired t-test (or Wilcoxon signed rank test for non-normal distribution. The same analysis will be done for all subscales of the SF-36 (see Table 8).

4.5.5. Analysis of secondary objective 4

For each country, the average HCRU and direct medical cost will be estimated along with its 95%CI (see Table 9).

4.5.6. Analysis of secondary objective 5

CCI

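### Objective 3 asks how LN affects HRQoL, but its planned analysis is a pooled one-year SF-36 change with no renal variable and no comparator, so it cannot answer that question.

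*Protocol*

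**What the plan says.** SAP 2.2.3 states the objective: "To assess impact of LN on HRQoL over a one-year period after diagnosis or enrolment". Protocol 2.2 has the same aim.

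Protocol 4.4.3 carries it out as follows: "This will be achieved by looking at changes in the SF-36 physical and mental components, and the total score at one year", by paired t-test or, for non-normal data, the Wilcoxon signed rank test. It then adds: "Changes over all the time period will be assessed using repeated measures analysis".

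SAP 4.5.4 narrows this to the total score and the subscales: "Changes in SF-36 total score from baseline to one year will be test for significance using the paired t-test", and "The same analysis will be done for all subscales of the SF-36". SAP Table 8 has columns for baseline, 12 months, change and p-value. Its rows are the total and the eight domains.

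Other relevant parts of the plan:

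- SF-36 is completed at Visit 1 and Visit 5 only (Protocol 3.2.3).
- Renal remission and renal laboratory results are planned for collection at 0, 3, 6, 9 and 12 months (Protocol 3.2.2), where available (Appendix 1 note).
- Recruitment aims for half the patients in remission and half not (Protocol 3.1 and 3.3).

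**The concern.** The objective asks about an effect of LN, but the analysis contains nothing that varies with LN. All patients have the disease, no population norm or other reference is named, and remission, proteinuria, SLEDAI-2K, LN class and refractory status appear neither as covariates nor as strata for SF-36.

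The plan does link disease status to other outcomes. Cost is to be stratified by disease activity (Protocol 3.1.6) and modelled on severity and activity (Protocol 4.5), and remission is the outcome for objective 2. HRQoL is the outcome left unlinked.

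The 50/50 enrolment target means that remission can be both gained and lost during the year. If SF-36 moves with renal status, these movements pull the mean change in opposite directions. At stake is whether objective 3 reports anything about LN at all.

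**Working it through.** **1. What each planned analysis contains**

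| Analysis | Where | Renal term? | Comparator? |
|---|---|---|---|
| Paired t-test or Wilcoxon, components and total | Protocol 4.4.3 | No | No |
| Repeated measures | Protocol 4.4.3 | None named | No |
| Paired t-test or Wilcoxon, total and subscales | SAP 4.5.4, Table 8 | No | No |

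With two SF-36 time points and no between-patient factor, repeated measures amounts to the same comparison as the paired test.

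**2. The plan's own figures**

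None exists for objective 3: no SD, effect size or power. The only power statement (N=200, 80%, 0.200 to 0.385) is for objective 2. It reproduces with the logistic-regression formula at a two-sided 5% level (N=200.8), but it says nothing about SF-36.

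**3. Structure**

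Let a share g gain remission and shift by +d points, a share l lose it and shift by −d, and the rest not shift. Then:

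- mean change = d(g − l)
- with x = +1, 0, −1 for gained, unchanged, lost: Var(x) = g + l − (g − l)²
- SE of the mean change = √[(s² + d²Var(x))/N], where s is the residual SD of change
- SE of the slope of change on x = s/√(N·Var(x))

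The mean is zero only if g = l (given equal and opposite shifts). Otherwise the offset is partial.

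**4. Illustration (all inputs assumed)**

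Take N=150 patients with both surveys, g=0.25, l=0.15, d=10, s=20 and a two-sided 5% test.

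- Mean change = 10 × (0.25 − 0.15) = 1.0.
- Var(x) = 0.40 − 0.01 = 0.39.
- Paired test: SE = √(439/150) = 1.71, power 9%.
- One-slope test: SE = 20/√58.5 = 2.61, ratio 10/2.61 = 3.8, power 97%.

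**5. Sensitivity to the shares**

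For N=150, d from 5 to 10 and s from 15 to 25:

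| Gain / lose | Paired test | One-slope test |
|---|---|---|
| 25% / 15% | 6–12% | 33% to over 99% |
| 10% / 5% | 5–7% | 16–88% |
| 30% / 5% | 9–48% | 26–99% |

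The 25%/15% row is itself demanding: from a 50/50 start, half of the non-remitters gain remission and 30% of the remitters lose it within a year.

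**6. Power of a four-group model**

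The one-slope test builds in symmetric effects. With separate groups, the step 4 inputs and a 50/50 start (before any gain from baseline adjustment):

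- gained (37.5) against stable out of remission (37.5): SE = 20√(2/37.5) = 4.62, power about 58%
- lost (22.5) against stable in remission (52.5): SE = 20√(1/22.5 + 1/52.5) = 5.04, power about 51%

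**The case against.** The strongest reply is that the study is descriptive by title, every patient has LN by design, and Protocol 4.4.3 itself says what the objective means: looking at SF-36 change. On that reading the paired test is adequate and only the word impact is loose. This stands as far as the remedy goes: rewording the objective is a legitimate repair. It does not rescue the present pairing of objective and analysis.

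Three stronger readings are tempting and are not supported:

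- A reader might infer that gains and losses cancel completely. The documents give no transition rates or SF-36 shifts, and complete cancellation needs them equal and opposite.
- A reader might take 97% against 9% as the measured cost of the planned test. It is one scenario on assumed inputs. The two tests address different hypotheses, and the 97% does not apply to a four-group model.
- A reader might look to SF-36 item 2 ("Compared to one year ago, how would you rate your health in general now") to fill the gap. It asks about general health and contains no LN measure, so it does not bear on this point.

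It is also fair to object that remission is an imperfect measure here. Its definition offers two proteinuria thresholds or physician discretion, visits are matched by proximity, and Protocol 3.1.4 assumes unchanged status after a missed visit, although SAP 4.3 says missing data are not imputed. Carrying status forward would inflate the stable groups. These points shape the fix; they do not remove the need for it.

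**Conclusion.** The mismatch holds and needs no assumption: objective 3, as analysed, has no renal term and no comparator, so the planned result describes one-year HRQoL under care in LN patients. A null result would not show that LN leaves HRQoL unaffected, and a non-null result could not be attributed to LN. The documents do not say that a null would be read as no impact; the point is that nothing in the plan guards against that reading.

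The size cannot be fixed from the documents. Under the assumptions in the working (N=150, shifts of 5 to 10 points, SD 15 to 25, three pairs of transition shares), power runs from about 5% to 48% for the paired test and from about 16% to over 99% for a one-slope linked test. Individual contrasts in a four-group model have roughly 50–60% in the step 4 scenario. The case for change is that the analysis should match the question, not a promised gain in power. It should be corrected before analysis, in proportion to a secondary objective.

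**What to change.** In SAP 4.5.4 and Table 8, keep the paired test and label it descriptive. Then add:

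- **Cross-sectional:** SF-36 by remission status at Visit 1.
- **Longitudinal:** a linear model of Visit 5 SF-36 on the Visit 1 score plus change in remission status (gained, lost, stable in, stable out), with estimates and 95% CIs.
- **Limited outcomes:** a small prespecified set of scores, for example the physical and mental components, with the domains as supportive. Protocol 4.4.3 names the components, but SAP 4.5.4 and Table 8 do not, so they would have to be added there.
- **One remission definition:** fixed in advance for this analysis by the study team.
- **Observed status only:** no carrying forward over missed visits, with the number of patients excluded for this reason reported.
- **Interpretation:** a statement that the result is an association.

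If the model is not added, reword objective 3 as: *describe one-year change in HRQoL in LN patients*.

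The cost is SAP wording and one extra table, with no new data. The downsides are association only, modest power per contrast, and possible misclassification of remission.
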